4. STUDY MEDICATION

For the purposes of this study, subjects enrolled will have been prescribed/authorized Spectrum Therapeutics products that are commercially available in participating countries. It is important to note that product availability varies from country to country. No country except Canada, has access to the full ST medical portfolio (e.g., only flowers are available in Germany).

The full repertoire of Spectrum Therapeutics products is outlined here (see Figure 1). It encompasses six “colors” (order from Red to Yellow follows the descending THC:CBD ratio), and five types of formulations: soft gels, spray*, oil, flowers and vapes). Refer to webpage for the most up to date products available per country <https://www.spectrumtherapeutics.com/canada/en/patients/products>.

Figure 1. Repertoire of Spectrum Therapeutics Products.

Cannabinoid Content for Spectrum Therapeutics Products			
Spectrum Product	Percentage of THC & CBD per gram of weight Dried flower (%)	Milligram of THC & CBD per milliliter of Oil (mg/ml)	Milligram of THC & CBD per Soft gel (mg)
Red 	(17-23) THC : (< 0.7) CBD	(26.3) THC : (<1) CBD	(2.5-10) THC : (<1) CBD
Orange 	(10-14) THC : (<1) CBD	NA	NA
Purple 	(8-11) THC : (< 0.7) CBD	NA	NA
Blue 	(6-10) THC : (8-11) CBD	(10) THC: (12-15) CBD	(2.5 – 10) THC : (1.75-15) CBD
Green 	(4-7) THC: (7-10) CBD	NA	NA
Yellow 	(<1) THC : (10-14) CBD	(<1) THC : (20) CBD	(<1) THC: (5-20) CBD

*Spray formulation is the most recent addition to the formulations and not yet featured on the web site.

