4.1 Study Medication Prescribing/Authorization

Medical cannabis is accessible to subjects via different authorization or prescription pathways, in different regional jurisdictions. Authorization and prescription are the two most common pathways.

In Canada, Spectrum Therapeutics products are authorized via the physician specifying the amount (in grams) of THC and/or CBD, and the subject is free to choose the product, licensed producer, and formulation on their own. Likewise, subjects have the freedom to switch from one product or producer to another, at will.

In other countries, such as Germany, medical cannabis products are prescribed, and physicians are specific in this process regarding parameters such as the licensed producer, mode of administration, and cannabinoid content (THC:CBD).

This protocol does not assign a specific intervention. The prescription of medical cannabis is decided by the subject and his or her physician prior to enrolling the subject in the study. The principal investigator has no control over the prescribing/authorization or administration of the cannabis product.

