4.2 Study Medication: Cannabinoid Content Calculation

On entering study medication information into *REDCap Cloud*, the preprogrammed algorithm will calculate the intake amount of mgs of THC and CBD for all formulations, and whether it was inhaled or ingested. Only limited data exist on the plasma concentration of circulating cannabinoids and their metabolites resulting from inhalation of cannabis products. It is known that factors influencing this include, but are not limited to, pattern of smoking or vaping (length of inhalation), as well as the flower combustion temperature. It is possible that these data may be calculated in retrospect (unlike other formulations that will allow for real time mg calculation), if more structured studies are conducted to evaluate the cannabinoid intake from smoked and/or vaped products, from different flower varieties.

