7. OUTCOME ASSESSMENTS

7.1 Study Endpoints

Primary endpoints

- Physician selection of Spectrum Therapeutics (ST) medical cannabis treatment regimen and changes over time in:
 - (1) average daily dose of THC and CBD (in mg);
 - (2) route of administration (inhaled or ingested).

Secondary endpoints

- Subject selection of ST treatment regimen and changes over time in:
 - (1) average daily dose of THC and CBD (in mg);
 - (2) route of administration (inhaled or ingested).
- Change in BPI-SF responses from baseline.
- Change in EQ5D-5L responses from baseline.
- PGI-C for the target treatment goal.
- CGI-I for the target treatment goal.
- In subjects taking an opioid, changes in opioid use over time (calculated as milligram morphine equivalents [MME]/day).
- Among subjects taking other medication, total daily dose change over time.

Safety endpoint

- Incidence of AEs stratified by product and formulation.

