Benzodiazepines Dosing Information

Name of drug _____

Daily dose of [baseline_visit][benzo1_name](total mg per day) _____

Check to add additional benzodiazepine medications

Name of drug _____

Daily dose of [baseline_visit][benzo2_name] (total mg per day) _____

Check to add additional benzodiazepine medications

Name of drug _____

Daily dose of [baseline_visit][benzo3_name] (total mg per day) _____

Opioid Dosing Information

Please enter MME (total daily morphine equivalent dose in mg) _____

Other Medication Information

Please indicate name of other drugs not included in the above classes _____

Daily dose (total mg per day), if available _____

ST Regimen Canada

[figure not shown]

Please enter in the table below total daily amount of Spectrum Therapeutics products consumed. Please be conscious of the units provided:

Inhaled cannabis = total number of inhalations per day

Ingested oils = total mL per day

Spray format = total number of sprays per day

Capsules & edibles = total number of capsules or total number of chocolate bar squares per day

	Inhaled Formats (dried flower, extract vaporizers) -- report daily total number of inhalations	Ingested Oil Formats - report daily total number of mLs	Spray Formats - report daily total number of sprays	Low Potency Capsule & Edible Formats - report daily total number of low-potency capsules (i.e. 2.5 mg), number of chocolate bar squares, etc.	High Potency Capsule Formats - report daily total number of high-potency capsules
Red (examples include Spectrum #1-4; Tweed Bakerstreet, Highlands, Houdstooth, Donegal; LBS Sunset)	 inhalations  	 mL  	 sprays  	 capsules  	 capsules  
Orange	 inhalations  		 sprays  		
Purple (examples include LBS Ocean View)	 inhalations  		 sprays  		
Blue (examples include Tweed Penelope)	 inhalations  	 mL  	 sprays  	 capsules  	 capsules  
Green (examples include Tweed Argyle)	 inhalations  	 mL  	 sprays  	 capsules  	 capsules  

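### The visible regimen forms count inhalations but record no flower mass, so a flower user's THC and CBD in mg/day rests on an assumed amount per inhalation

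*Protocol*

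**What the plan says.** Section 7.1 sets the primary endpoint as the physician's choice of regimen and its change over time, expressed as "average daily dose of THC and CBD (in mg") and route.

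Figure 1 in Section 4 gives flower strength under the column "Percentage of THC & CBD per gram of weight Dried flower"; the entry for Red is ("17-23) THC : (< 0.7) CBD". Oils are given in mg per mL and soft gels in mg per unit.

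The regimen grid in Appendix 1 instructs: "Inhaled cannabis = total number of inhalations per day". Its column heading is "Inhaled Formats (dried flower, extract vaporizers) -- report daily total number of inhalations", so flower and extract share one count per colour. The same grid appears in Appendices 2 and 3. All three are headed ST Regimen Canada.

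If an inhaled product is entered, the form also asks for the most common method (smoked, flower vaporizer or extract vaporizer) and, if known, the vaporizer temperature. It then shows a calculated daily dose in mg for inhaled THC and CBD, described as approximate. The equation sits behind a link and is not reproduced.

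Section 4.2 says the algorithm will produce mg for every formulation and classify it as inhaled or ingested. The same paragraph then says little is known about cannabinoid levels after inhalation, and that these figures may have to be worked out retrospectively, in contrast to the other formulations.

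**The concern.** For oils and soft gels, the unit entered (mL, capsules) matches the unit of labelled content (mg per mL, mg per soft gel), so mg per day follows directly. For flower the two do not meet: content is per unit weight, but the entry is a number of inhalations. The missing link is the mass of flower per inhalation.

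This matters because the quantity is part of the primary endpoint. It affects a subject who uses one flower product of known strength, so it is separate from the problem of mixed products. It also affects change over time. With method and temperature unchanged, a subject who takes larger puffs at the same count shows no change in dose, and one who takes more but smaller puffs of the same amount of flower shows a rise. A statistical analysis plan cannot repair this, because the quantity is never collected.

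**Working it through.** The protocol states no mg-per-inhalation figure, so there is no figure of its own to reproduce. The check is one of units.

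**Formula.** mg/day = (inhalations per day) × (mg flower per inhalation) × (content fraction)

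| Term | Source | Available? |
|---|---|---|
| Inhalations per day | Appendices 1 to 3, regimen grid | Yes |
| mg flower per inhalation | none | No |
| Content fraction | Figure 1 (Red: 17-23% THC, i.e. 170-230 mg/g) | Yes, as a range |

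The other visible inhaled inputs are colour, most common method and vaporizer temperature. None of them is a mass. Whatever the hidden equation does with them, its amount per inhalation is assumed, not measured.

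**Illustration.** Mass per inhalation is not in the documents, so two assumed ranges are shown, both for ten inhalations a day of Red flower.

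- At 0.02-0.10 g per inhalation: lower end 10 × 0.02 g × 170 mg/g = 34 mg; upper end 10 × 0.10 g × 230 mg/g = 230 mg. Ratio 230/34 = 6.8, which is 5 (mass) × 1.35 (label).
- At 5-50 mg per inhalation: lower end 10 × 5 mg × 0.17 = 8.5 mg; upper end 10 × 50 mg × 0.23 = 115 mg. Ratio 115/8.5 = 13.5, which is 10 (mass) × 1.35 (label).

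On the second range, ten inhalations of Blue flower (6-10% THC, 8-11% CBD) hold 3-50 mg THC and 4-55 mg CBD.

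**With grams recorded.** At an illustrative 0.5 g/day of Red flower, content is 0.5 g × 170-230 mg/g = 85-115 mg. The ratio is 23/17 = 1.35, from the label range alone and before any self-report error.

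The fold ranges depend on the masses assumed. The structure does not: recording grams removes one unmeasured multiplier.

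**Section 4.2 against the forms.** Section 4.2 first promises mg for all formulations, then says inhaled figures may come only in retrospect. The forms nevertheless display an inhaled mg value at entry. A retrospective calculation would still need the flower mass or an assumption in its place.

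**The case against.** The best defence is that the sponsor knowingly chose a practical unit for a real-world registry and partly said so: the form calls its result approximate, and Section 4.2 admits the difficulty with inhaled products. Grams are not error-free either. They would be self-reported, and they give the content of flower used, which is not the amount delivered or absorbed. All of this stands, and it limits what the fix can claim. Disclosure does not, however, supply the missing term.

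A reader might also infer four stronger things that the document does not support.

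- *That physicians authorise flower by weight, and that this choice is lost.* Section 4.1 says products in Canada are "authorized via the physician specifying the amount (in grams) of THC and/or CBD". That is grams of cannabinoid, for the products generally, not grams of flower.
- *That Section 4.2 itself says mass per inhalation varies.* It names "pattern of smoking or vaping (length of inhalation") among factors that influence plasma concentration. It says nothing about flower mass.
- *That the conversion is the count times one fixed constant.* The equation is not visible, and method or temperature may enter it. Method is asked again at follow-up, so a change in the most common method would be recorded.
- *That all German dose data are affected.* Section 4 says only flowers are available in Germany, but the regimen forms shown are the Canadian ones. For countries such as Germany, Section 4.1 describes prescriptions that specify "the licensed producer, mode of administration, and cannabinoid content (THC:CBD"), with no gram unit. Whether the German form shares the gap cannot be checked.

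**Conclusion.** The point holds as a unit gap on the visible Canadian forms. Flower content is by weight, inhaled quantity is a count, and nothing visible connects the two, so the displayed inhaled mg for flower users rests on an assumed amount per inhalation. Section 4.2 is also inconsistent on whether inhaled mg will be available at entry.

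The size cannot be fixed from the document. The 6.8-fold and 13.5-fold spreads illustrate two assumed mass ranges and are not estimates of error in this registry. The 1.35-fold comparator for Red flower is a best case with accurately reported grams. The ingested part of the endpoint is not affected by this point.

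It is worth correcting because it concerns the primary endpoint, the missing quantity cannot be recovered afterwards, and the change is small.

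**What to change.** 1. For dried flower, add a grams-per-day field to the regimen forms: the recommended amount at physician visits and the amount used at subject follow-ups.
2. Compute mg for flower as grams × labelled percentage, and label the result as cannabinoid content of product used, not delivered or absorbed dose.
3. Keep the inhalation count as a descriptive item. Because flower and extract share one count, keep the grams field specific to flower so that the two are not mixed.
4. Reconcile Section 4.2 with the inhaled mg fields that the forms fill at entry.
5. Check whether the regimen forms for other countries, Germany in particular, have the same gap.

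The cost is one or two numeric fields per flower row and a changed formula; treatment is not altered. The downsides are that grams are self-reported and miss delivery losses. The change does not settle extract vaporizers, for which Figure 1 shows no content.

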Appendix 2 – PHYSICIAN-VERIFIED FOLLOW-UP ASSESSMENT

ST Regimen Canada

[figure not shown]
[figure not shown]

[figure not shown]
[figure not shown]

[figure not shown]
[figure not shown]

[figure not shown]
[figure not shown]

Please enter in the table below total daily amount of Spectrum Therapeutics products consumed. Please be conscious of the units provided:

Inhaled cannabis = total number of inhalations per day

Ingested oils = total mL per day

Spray format = total number of sprays per day

Capsules & edibles = total number of capsules or total number of chocolate bar squares per day

Physician-recommended Regimen of Spectrum Therapeutics Products					
	Inhaled Formats (dried flower, extract vaporizers) -- report daily total number of inhalations	Ingested Oil Formats - report daily total number of mLs	Spray Formats - report daily total number of sprays	Low Potency Capsule & Edible Formats - report daily total number of low-potency capsules (i.e. 2.5 mg), number of chocolate bar squares, etc.	High Potency Capsule Formats - report daily total number of high-potency capsules
Red (examples include Spectrum #1-4; Tweed Bakerstreet, Highlands, Houdstooth, Donegal; LBS Sunset)	 inhalations  	 mL  	 sprays  	 capsules  	 capsules  
Orange	 inhalations  		 sprays  		
Purple (examples include LBS Ocean View)	 inhalations  		 sprays  		
Blue (examples include Tweed Penelope)	 inhalations  	 mL  	 sprays  	 capsules  	 capsules  
Green (examples include Tweed Argyle)	 inhalations  	 mL  	 sprays  	 capsules  	 capsules  
Yellow (examples include Tweed CBD Softgels)	 inhalations  	 mL  	 sprays  	 capsules  	 capsules  
Spectrum Clear (or White)		 mL  			

You indicated that your patient has been recommended an inhaled format. Please identify their most common method of administration.
(*inhal_admin*)
[Branching logic exists]

- Smoked
 Dried flower vaporizer (e.g. Stroz and Bickel, PAX)
 Extract vaporizer (e.g. vape pen cartridge)

Do you or your patient know the temperature set point of the vaporizer (in °C)
(*inhal_vape_Y/N*)
[Branching logic exists]

- Yes
 No

If known, please provide the temperature set point of your patient's vaporizer (in °C) _____
(*inhal_vape_temp*)
(125 / 300)
[Branching logic exists]

Calculated, approximated total daily dose of THC and CBD (in mgs)

	THC	CBD
Inhaled	(inhal_THC)  View Equation	(inhal_CBD)  View Equation
Ingested	(ingest_THC)  View Equation	(ingest_CBD)  View Equation

Concomitant medication

Concomitant medication - Existing

Existing NSAIDs and Acetaminophen Dosing Information

At last visit, you indicated that your patient was taking [baseline_visit][nsaid1_name]. Is your patient still taking this medication?

- Yes
 No

What is their current daily dose of [baseline_visit][nsaid1_name] (total mg per day)?

Please select the reason why your patient stopped taking this medication.

- Side effects
 Cost
 Lack of benefit
 No longer needs/ replaced by medical cannabis
 Unknown

At last visit, you indicated that your patient was taking [baseline_visit][nsaid2_name]. Is your patient still taking this medication?

- Yes
 No

Please select the reason why your patient stopped taking this medication.

- Side effects
 Cost
 Lack of benefit
 No longer needs/ replaced by medical cannabis
 Unknown

What is their current daily dose of [baseline_visit][nsaid2_name] (total mg per day)?

At last visit, you indicated that your patient was taking [baseline_visit][nsaid3_name]. Is your patient still taking this medication?

- Yes
 No

Please select the reason why your patient stopped taking this medication.

- Side effects
- Cost
- Lack of benefit
- No longer needs/ replaced by medical cannabis
- Unknown

What is their current daily dose of [baseline_visit] [nsaid3_name] (total mg per day)?

Existing Antidepressants Dosing Information

At last visit, you indicated that your patient was taking [baseline_visit][antidep1_name]. Is your patient still taking this medication?

- Yes
- No

Please select the reason why your patient stopped taking this medication.

- Side effects
- Cost
- Lack of benefit
- No longer needs/ replaced by medical cannabis
- Unknown

What is their current daily dose of [baseline_visit] [antidep1_name] (total mg per day)?

At last visit, you indicated that your patient was taking [baseline_visit][antidep2_name]. Is your patient still taking this medication?

- Yes
- No

Please select the reason why your patient stopped taking this medication.

- Side effects
- Cost
- Lack of benefit
- No longer needs/ replaced by medical cannabis
- Unknown

What is their current daily dose of [baseline_visit]
[antidep2_name] (total mg per day)?

At last visit, you indicated that your patient was taking
[baseline_visit][antidep3_name]. Is your patient still taking this
medication?

- Yes
 No

Please select the reason why your patient stopped taking this
medication.

- Side effects
 Cost
 Lack of benefit
 No longer needs/ replaced by medical
cannabis
 Unknown

What is their current daily dose of [baseline_visit]
[antidep3_name] (total mg per day)?

Existing Anticonvulsants Dosing Information

At last visit, you indicated that your patient was taking
[baseline_visit][anticon1_name]. Is your patient still taking this
medication?

- Yes
 No

Please select the reason why your patient stopped taking this
medication.

- Side effects
 Cost
 Lack of benefit
 No longer needs/ replaced by medical
cannabis
 Unknown

What is their current daily dose of [baseline_visit]
[anticon1_name] (total mg per day)?

At last visit, you indicated that your patient was taking
[baseline_visit][anticon2_name]. Is your patient still taking this
medication?

- Yes
 No

Please select the reason why your patient stopped taking this medication.

- Side effects
- Cost
- Lack of benefit
- No longer needs/ replaced by medical cannabis
- Unknown

What is their current daily dose of [baseline_visit] [anticon2_name] (total mg per day)?

At last visit, you indicated that your patient was taking [baseline_visit][anticonvu3_name]. Is your patient still taking this medication?

- Yes
- No

Please select the reason why your patient stopped taking this medication.

- Side effects
- Cost
- Lack of benefit
- No longer needs/ replaced by medical cannabis
- Unknown

What is their current daily dose of [baseline_visit] [anticonvu3_name] (total mg per day)?anticon1_dose_follow1

Existing Muscle Relaxants Dosing Information

At last visit, you indicated that your patient was taking [baseline_visit][musrel1_name]. Is your patient still taking this medication?

- Yes
- No

Please select the reason why your patient stopped taking this medication.

- Side effects
- Cost
- Lack of benefit
- No longer needs/ replaced by medical cannabis
- Unknown

What is their current daily dose of [baseline_visit]
[musrel1_name] (total mg per day)?

At last visit, you indicated that your patient was taking
[baseline_visit][musrel2_name]. Is your patient still taking this
medication?

- Yes
- No

Please select the reason why your patient stopped taking this
medication.

- Side effects
- Cost
- Lack of benefit
- No longer needs/ replaced by medical
cannabis
- Unknown

What is their current daily dose of [baseline_visit]
[musrel2_name] (total mg per day)?

At last visit, you indicated that your patient was taking
[baseline_visit][musrel3_name]. Is your patient still taking this
medication?

- Yes
- No

Please select the reason why your patient stopped taking this
medication.

- Side effects
- Cost
- Lack of benefit
- No longer needs/ replaced by medical
cannabis
- Unknown

What is their current daily dose of [baseline_visit]
[musrel3_name] (total mg per day)?

Existing Benzodiazepines Dosing Information

At last visit, you indicated that your patient was taking
[baseline_visit][benzo1_name]. Is your patient still taking this
medication?

- Yes
- No

Please select the reason why your patient stopped taking this medication.

- Side effects
- Cost
- Lack of benefit
- No longer needs/ replaced by medical cannabis
- Unknown

What is their current daily dose of [baseline_visit] [benzo1_name] (total mg per day)?

At last visit, you indicated that your patient was taking [baseline_visit][benzo2_name]. Is your patient still taking this medication?

- Yes
- No

Please select the reason why your patient stopped taking this medication.

- Side effects
- Cost
- Lack of benefit
- No longer needs/ replaced by medical cannabis
- Unknown

What is their current daily dose of [baseline_visit] [benzo2_name] (total mg per day)?

At last visit, you indicated that your patient was taking [baseline_visit][benzo3_name]. Is your patient still taking this medication?

- Yes
- No

Please select the reason why your patient stopped taking this medication.

- Side effects
- Cost
- Lack of benefit
- No longer needs/ replaced by medical cannabis
- Unknown

What is their current daily dose of [baseline_visit] [benzo3_name] (total mg per day)?

Existing Opioid Dosing Information

At last visit, you indicated that your patient had an MME of [baseline_visit][opioid_mme]. Is your patient still taking opioids?

- Yes
- No

Please select the reason why your patient stopped taking this medication.

- Side effects
- Cost
- Lack of benefit
- No longer needs/ replaced by medical cannabis
- Unknown

What is their current MME?

Existing Other Medications Dosing Information

At last visit, you indicated that your patient was taking other medications, including [baseline_visit][othmed_name]. Is your patient still taking any of these other prescription medications?

- Yes
- No

Please describe any **changes** to their other existing prescription medications since last visit (including changes to total daily dose)

Concomitant Medications - New

Since last visit, has your patient **started** taking any of the following classes of prescription medication (select all that apply)

- Nonsteroidal Anti-inflammatory Drugs (NSAIDs) and Acetaminophen
- Antidepressants (TCA, SNRI, SSRI)
- Anticonvulsants (gabapentin, pregabalin)
- Muscle Relaxants
- Benzodiazepines
- Opioids
- Other
- Medical Cannabis from a Licensed Producer other than Spectrum

Name of new NSAID/Acetaminophen medication (started since last visit)

Daily dose of [physician_1st_follow][nsaid4_name] (total mg per day)

Name of new antidepressant medication (started since last visit)

Daily dose of [physician_1st_follow][antidep4_name] (total mg per day)

Name of new anticonvulsant medication (started since last visit)

Daily dose of [physician_1st_follow][anticon4_name] (total mg per day)

Name of new muscle relaxant medication (started since last visit)

Daily dose of [physician_1st_follow][musrel4_name] (total mg per day)

Name of new benzodiazepine medication (started since last visit)

Daily dose of [physician_1st_follow][benzo4_name] (total mg per day)

Please enter MME (total daily morphine equivalent dose in mg)

Name of new prescription medication (started since last visit, not covered in above classes)

Daily dose of [physician_1st_follow][othmed4_name] (total mg per day)

Physician AE form

Product information

Do you have any adverse events to report related to this patient?

- Yes
- No

Suspect product(s) name

Start date

_____ (YYYY-MM-DD)

End date

_____ (YYYY-MM-DD)

Route of administration

- oral - oil
- oral - softgel
- oral - spray
- oral - beverage
- oral - chocolate
- oral
- inhalation - smoked
- inhalation - vaporized
- inhalation

Dose (please include amount and unit i.e. mg, ml, #softgels, #inhalations, etc.)

Did reaction disappear after reducing the dose or stopping the product ?

- No
- Yes
- Unknown

Did reaction reappear after same product/treatment was restarted?

- No
- Yes
- Unknown

AE description

Onset date of event

(YYYY-MM-DD)

End date of event

(YYYY-MM-DD)

Select seriousness criteria

- Non-serious
- Death
- Life-Threatening
- Inpatient/Prolonged Hospitalization
- Congenital Anomaly/Birth Defect
- Persistent of Significant Disability /Incapacity
- Other Medically Important Condition

Admission date

(YYYY-MM-DD)

Discharge date

(YYYY-MM-DD)

Date of death

(YYYY-MM-DD)

Cause of death

Was an autopsy performed?

- Yes
- No

Please provide autopsy results

Select outcome of event(s)

- Recovered
- Recovering
- Ongoing
- Fatal
- Unknown

Select severity

- Mild
- Moderate
- Severe

Investigator Causality Assessment:

- Related
- Probable
- Possible
- Unlikely
- Not related

Please describe alternate possible causes for the AE?

Please provide patients medical history

Please provide a summary of the patients course during the time of the event (AE, symptoms, events chronology, treatments, medical history, titration information, outcome per event, etc.).

CGI-I

Clinician Global Impression of Improvement

Since the start of Spectrum Therapeutics treatment, my patient's overall symptom status is:

(best describe how your patient's symptom is now, compared with how it was before they began taking medical cannabis)

- Very Much Improved -nearly all better; good level of functioning; minimal symptoms; represents a very substantial change
- Much Improved -notably better with significant reduction of symptoms; increase in the level of functioning but some symptoms remain
- Minimally Improved -slightly better with little or no clinically meaningful reduction of symptoms. Represents very little change in basic clinical status, level of care, or functional capacity
- No Change -symptoms remain essentially unchanged
- Minimally Worse -slightly worse but may not be clinically meaningful; may represent very little change in basic clinical status or functional capacity
- Much Worse -clinically significant increase in symptoms and diminished functioning
- Very Much Worse -severe exacerbation of symptoms and loss of functioning

Patient reported outcomes

BPI

Throughout our lives, most of us have had pain from time to time (such as minor headaches, sprains, and toothaches). Have you had pain other than these everyday kinds of pain today?

- Yes
- No

Please select the number (0= no pain, 10= pain as bad as you can imagine) that best describes your pain at its worst in the last 24 hours.

- 0
- 1
- 2
- 3
- 4
- 5
- 6
- 7
- 8
- 9
- 10

Please select the number (0= no pain, 10= pain as bad as you can imagine) that best describes your pain at its least in the last 24 hours.

- 0
- 1
- 2
- 3
- 4
- 5
- 6
- 7
- 8
- 9
- 10

Please select the number (0= no pain, 10= pain as bad as you can imagine) that best describes your pain on the average.

- 0
- 1
- 2
- 3
- 4
- 5
- 6
- 7
- 8
- 9
- 10

Please select the number (0= no pain, 10= pain as bad as you can imagine) that best describes how much pain you have right now.

- 0
- 1
- 2
- 3
- 4
- 5
- 6
- 7
- 8
- 9
- 10

Please select the number (0= does not interfere, 10= completely interferes) that best describes how, during the past 24 hours, pain has interfered with your: **General Activity**

- 0
- 1
- 2
- 3
- 4
- 5
- 6
- 7
- 8
- 9
- 10

Please select the number (0= does not interfere, 10= completely interferes) that best describes how, during the past 24 hours, pain has interfered with your: **Mood**

- 0
- 1
- 2
- 3
- 4
- 5
- 6
- 7
- 8
- 9
- 10

Please select the number (0= does not interfere, 10= completely interferes) that best describes how, during the past 24 hours, pain has interfered with your: **General Activity**

- 0
- 1
- 2
- 3
- 4
- 5
- 6
- 7
- 8
- 9
- 10

Please select the number (0= does not interfere, 10= completely interferes) that best describes how, during the past 24 hours, pain has interfered with your: **Mood**

- 0
- 1
- 2
- 3
- 4
- 5
- 6
- 7
- 8
- 9
- 10

Please select the number (0= does not interfere, 10= completely interferes) that best describes how, during the past 24 hours, pain has interfered with your: **Walking ability**

- 0
- 1
- 2
- 3
- 4
- 5
- 6
- 7
- 8
- 9
- 10

Please select the number (0= does not interfere, 10= completely interferes) that best describes how, during the past 24 hours, pain has interfered with your: **Normal work (includes both work outside the home and housework)**

- 0
- 1
- 2
- 3
- 4
- 5
- 6
- 7
- 8
- 9
- 10

Please select the number (0= does not interfere, 10= completely interferes) that best describes how during the past 24 hours, pain has interfered with your: **Relations with other people**

- 0
- 1
- 2
- 3
- 4
- 5
- 6
- 7
- 8
- 9
- 10

Please select the number (0= does not interfere, 10= completely interferes) that best describes how during the past 24 hours, pain has interfered with your: **Sleep**

- 0
- 1
- 2
- 3
- 4
- 5
- 6
- 7
- 8
- 9
- 10

Please select the number (0= does not interfere, 10= completely interferes) that best describes how during the past 24 hours, pain has interfered with your: **Enjoyment of life**

- 0
- 1
- 2
- 3
- 4
- 5
- 6
- 7
- 8
- 9
- 10

EQ5D

Mobility

- I have no problems in walking about
- I have slight problems in walking about
- I have moderate problems in walking about
- I have severe problems in walking about
- I am unable to walk

Self-Care

- I have no problems washing or dressing myself
- I have slight problems washing or dressing myself
- I have moderate problems washing or dressing myself
- I have severe problems washing or dressing myself
- I am unable to wash or dress myself

Usual Activities

- I have no problems doing my usual activities
- I have slight problems doing my usual activities
- I have moderate problems doing my usual activities
- I have severe problems doing my usual activities
- I am unable to do my usual activities

Pain/Discomfort

- I have no pain or discomfort
- I have slight pain or discomfort
- I have moderate pain or discomfort
- I have severe pain or discomfort
- I have extreme pain or discomfort

Anxiety/Depression

- I am not anxious or depressed
- I am slightly anxious or depressed
- I am moderately anxious or depressed
- I am severely anxious or depressed
- I am extremely anxious or depressed

We would like to know how good or bad your health is TODAY. Please write a number between 0 and 100.

100 means the best health you can imagine

0 means the worst health you can imagine

PGI-C

Global Impression of Change

Since the start of Spectrum Therapeutics treatment, my overall symptom status is:

(best describe how your symptom is now, compared with how it was before you began taking medical cannabis)

- Very Much Improved
- Much Improved
- Minimally Improved
- No Change
- Minimally Worse
- Much Worse
- Very Much Worse

